3. STUDY DESIGN

We will conduct a RCT to evaluate improvement in function with PE-PC compared to PCMHI-TAU among Veterans with PTSD symptoms in PC (see Figure 2 for RCT study flow). Veterans presenting in PC with chronic PTSD symptoms of at least 3 months duration who meet minimal inclusion/exclusion criteria will be randomly assigned to PE-PC (four to six, 30-minute in person or telehealth sessions) or PCMHI-TAU over 4-6 weeks. TAU will include the current standard of PTSD care in PCMHI (medication, referral to specialty MH, etc.). The type of TAU used will reflect the current practice in PCMHI and will not be constrained in the study design. All care received will be closely monitored and recorded. All Veterans will complete a baseline assessment (week 0) prior to randomization and follow-up assessments at weeks 6 (post), 12, and 24 post-baseline. Primary outcome will be the total score of World Health Organization Disability Assessment Schedule (WHODAS). Secondary outcomes will be Brief Inventory of Psychosocial Function (B- IPF), Clinician Administered PTSD Scale-5 (CAPS5) and Patient Health Questionnaire-9 (PHQ-9). If WHODAS shows floor or ceiling effect, the overall impairment score of the B-IPF will be used as a primary outcome measure.

To achieve these objectives, the study will have two phases. Phase one will include regulatory start-up and review, as well as study team training for coordinators, PCMHI providers, evaluators, and the rest of the PCMHI team. [name] and [name] have an established training protocol and will augment with

training case recording ratings to establish competence prior to the therapist seeing randomized study patients. This process will be facilitated since the recruiting site already has many of the staff as providers. Phase two will be an RCT of functional outcomes for PE-PC compared to PCMH-TAU in PC patients with PTSD. Veterans who present in VHA PC with PTSD symptoms who meet minimal inclusion criteria will be randomly assigned to receive PE-PC or PCMH-TAU. Primary outcome will be function of WHODAS) assessed at baseline, week 6, week 12, and week 24. Utilization of MH and overall VHA services will also be examined. Secondary outcomes will include PTSD severity (CAPS5) and depressive symptoms. RCT outcomes will be examined using linear modeling.

FIGURE 2. Study Design

Treatment Conditions.

- 1. Experimental Condition: Prolonged Exposure for Primary Care (PE-PC).** PE-PC will be provided by the PCMH or research provider in four to six, 30-minute appointments scheduled approximately once a week over 4-6 weeks (to accommodate scheduling and missed appointments). PCMH providers of PE-PC will include research clinicians, VA psychologists, social workers, and psychiatric nurses who have completed the PE training program and are on the IRB personnel list. Treatment will follow the PE-PC manual and Veteran workbook developed in the pilot

study, with minor modifications that will occur in our first 3 months of the study for use in VHA. Treatment content was drawn from the PE model. PE components include: imaginal exposure, in vivo exposure, psychoeducation, and processing. These four components are all included in PE-PC at a lower “dose” based on repetition or duration of session. Breathing was not included based on dismantling research showing no benefit and possible interference with outcome in other anxiety disorder, such as panic disorder. At the first 30-minute appointment, the PCMHI provider will review the “Confronting Uncomfortable Memories” activity workbook to be completed at home and brought back for use in subsequent appointments. The workbook asks the Veteran to write a detailed first-person narrative of the event associated with the greatest level of current distress, including recollection of personal thoughts, feelings, and physical reactions. Emotional processing questions are also included. In addition, the PCMHI provider will plan for in-vivo exposure activities between appointments. The Veteran will be instructed to complete the memory exposure for 30 minutes each day between appointments. At the second 30-minute appointment, the PCMHI provider will review the Veteran’s exposures, problem-solve any implementation difficulties, and process the exercises. The Veteran will then read the narrative and his or her answers to the emotional processing questions out loud and they will process the exercise. Practice continues between sessions. This appointment format and content are repeated in the subsequent appointments. At the end of treatment, the provider and Veteran will review treatment progress assisted by results of the PCL-5 administered at baseline and during the final appointment. Possible outcomes of this collaborative review are to conclude treatment at four-six appointments or refer the Veteran to specialty MH care for more intensive treatment.

Provider Training. Drs. [name], [name], and [name] have an established training protocol and will augment this protocol with training case recording ratings to establish competence prior to therapists seeing randomized study patients. [name] as the lead for the PE Therapy Roll Out has extensive experience in fidelity assessment and training to criterion. [name] has been leading the implementation of PE-PC in MTFs in his pilot study and randomized trial. He has years of experience training military providers in this model. Evident within this team is extensive experience working with trauma survivors and expertise in training providers in rapport building within this population as well as manualized therapy components. [name] is the developer of PE and will provide her expertise and input into the design and implementation of training. [name] worked with [name] and [name] on the development of PE-PC protocol. She has been a PE trainer since 2000. Therapists will be trained to a minimal 85% competency on the PE-PC fidelity manual elements prior to seeing randomized cases. While this is a high bar, the brief intervention requires a high level of competence.

Evaluation of PE-PC Fidelity. Treatment fidelity will be assessed by review of a randomly selected 10% of recorded session tapes by a trained fidelity evaluator. In addition, training tapes will be rated for fidelity to ensure therapists are competent prior to their receiving randomized cases. [name] will lead weekly ongoing supervision for PE-PC therapists for the duration of the trial to further ensure consistent therapist competence and fidelity. [name] was trained in PE by [name] and has extensive experience in delivery of and supervision in PE therapy, both in the context of RCTs and routine VA clinical settings.

2. **Control Condition: Treatment as Usual Condition.** Veterans assigned to PCMHI-TAU will receive standard PCMHI care for PTSD in PC that does not include any PTSD-specific therapy in PCMHI but may include referral for specialty care (including specialty MH), medication management or general supportive contact while awaiting referral. All PTSD care received during the study will be

collected and monitored as TAU. TAU will include the current standard of PTSD care in PCMH (medication, referral to specialty MH, etc.). The type of TAU used will reflect the current practice in PCMH and will not be constrained in the study design. All care will be recorded when a research assistant (RA) conducts a monthly standardized Computerized Patient Record System (CPRS) records review of all MH care received. Each encounter in CPRS will be noted for all randomized patients. Encounter current procedural terminology (CPT) codes, billing codes, duration or contacts will be tracked. No shows and cancellations will also be tracked. Finally, psychoactive medications will be tracked on a monthly basis as well, including medications prescribed, changes, and whether the prescriptions have been filled. While this is most relevant for the TAU condition, these monthly treatment reviews will be conducted on all enrolled Veterans to ensure we can compare rates across groups and note compliance with study requirements.

4. INCLUSION AND EXCLUSION CRITERIA / STUDY POPULATION

Veterans presenting in PC with chronic PTSD symptoms (PCL-5S ≥ 28) of at least 3 months duration who meet minimal inclusion/exclusion criteria will be randomly assigned to PE-PC (four to six, 30-minute sessions) or PCMH-TAU over 4-6 weeks. Non-veterans will not be included in the study. All Veterans will complete a baseline assessment prior to randomization and post- treatment and follow-up assessments at Weeks 6, 12, and 24 post-baseline. Interview assessments will be completed via phone or face-to-face depending on patient preference. Self-reports will be completed via paper and pencil or online via REDCap. Potential Veteran participants will be any era Veterans with PTSD symptoms and desire treatment for this issue. Age range will include 18 to 70. Ralph H. Johnson VAMC (CHS and surrounding CBOCs) PCMH will conduct the study.

Inclusion Criteria:

1. Any era Veterans seeking care in VA PC for PTSD symptoms (PCL-5 ≥ 28).
2. Age 18-70.
3. English speaking.
4. Report significant impairment in function related to PTSD symptoms as noted on intake WHODAS.
5. Report that they want treatment for PTSD.

Exclusion Criteria:

1. Other primary clinical issue that would interfere with PTSD treatment.
2. Level of suicidal risk as determined by the Columbia Suicide Severity Rating Scale (C-SSRS) that requires intervention.
3. Severe cognitive impairment that, in the judgment of the investigator, makes it unlikely that the patient can adhere to the study regimen.
4. Psychosis or unmanaged bipolar disorder.
5. Moderate to severe substance use disorder in the past 8 weeks.
6. Patients who are currently receiving talk therapy for trauma- related symptoms.

Inclusion/Exclusion criteria will initially be determined by the PCMH provider at the first contact and will be confirmed by the Independent Evaluator (IE) at the Baseline assessment following consent.

Medication Stabilization. Participants meeting inclusion criteria will be asked to maintain medications at current dosages when medically appropriate. Participants who have not initiated new psychotropic prescription medications in the previous 2 weeks will complete the baseline assessment battery. Potential participants who have recently begun trials of psychotropic prescription medication will be required to wait 2 weeks prior to completing the baseline assessment battery to ensure medication stabilization, at which point the assessment battery will be administered (or re-administered if applicable). This re-administered battery will be used for pre-treatment data in analyses.

6. NUMBER OF SUBJECTS

To account for attrition during treatment (estimated at 15%), and loss to follow-up (estimated at 10%), and consented screen fails (estimated at 30%) we inflate the sample size to approximately 267 subjects to achieve a final sample size of approximately 120 subjects: 267 less 30% consented screen fails = 187; 187 less 15% attrition = 147; 147 less 10% loss to follow-up = 120 total participants completing all measures.

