images will be stored on the secure VA research network. Participants will then be asked to mail back the completed, signed consent form in the return envelope provided.

Per VA Directive 6609 instructions for mailing sensitive materials, study staff will attach a notice with the following language on the front of any mailed consent paperwork, and instruct participants to attach it to the completed paperwork to be returned:

NOTICE!!!

1. Access to these records is limited to: AUTHORIZED PERSONS ONLY.
2. Information may not be disclosed from this file unless permitted by all applicable legal authorities, which may include the Privacy Act; 38 U.S.C. §§ 5701, 5705, 7332; the Health Insurance Portability and Accountability Act; and regulations implementing those provisions, at 38 C.F.R. §§ 1.460 – 1.599 and 45 C.F.R. Parts 160 and 164.
3. Anyone who discloses information in violation of the above provisions may subject to civil and criminal penalties.

To mitigate risk, study staff will instruct the participant to only sign those areas of the consent/HIPAA that must be in the participant's handwriting. Other areas of the forms (such as the name of the participant and date at the top of each page of the consent) will be completed by study staff once the paperwork is returned. Note that study staff expects this form of consent to be rare, and will only be offered to participants with unavoidable barriers that prevent them or study staff from consenting in person. Absolutely no study procedures will begin until study staff completes the consent process.

Randomization Procedures. A randomized block randomization schedule will be generated. Participants will be randomly assigned (1:1) to one of the two study conditions. After determining eligibility, enrolled patients will be randomized to treatment groups using a web-based computer generated randomization scheme. The randomization results then will be recorded on the master tracking table. Randomization will occur at the patient level. Once a patient is randomized and attends the first session, he or she will be entered into the study and included in the intent-to-treat analysis plan. The only members of the research team who will be aware of randomization assignment will be the project therapists, the research assistant and coordinator, and the statistical analyst in charge of randomization.

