Power Analysis. We propose to enroll 120 patients (60 per group) and considered power to detect a clinically meaningful difference in primary outcome at 6 months. The sample size is expected to have 80% power to detect a 0.54 standardized effect size with 0.05 two-sided tests for the outcome of WHODAS total score, assuming 10% lost- to-follow-up at the primary endpoint of 6 weeks post-baseline. This estimate of loss to follow-up may seem low but the period of follow-up is short and patients will be followed regardless of treatment completion to fully model response. The between-

group standardized effect size of 0.54 is approximately a medium effect size and is meaningful for both function and symptoms, and we consider this effect size minimally detectable with PE-PC based on our preliminary data. If no differential trends between arms is present over the 24 weeks follow-up time, we will be able to detect a smaller standardized effect size of 0.49 as a time-averaged between- arm difference with a 0.05 level two-sided test assuming within-person correlation of 0.6 and an overall 20% loss to follow-up by week 24 based on our preliminary data. For binary outcome of remission, we do not have preliminary data, but we note that we do not expect to have adequate power unless the between-arm difference in remission is very large; for example, the study will have 80% power to detect a difference of 69% vs. 42% with a 0.05 level two-sided test.

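### Section 6's recruitment arithmetic does not follow from its stated rates, and its 120 are completers while the power section's 120 are patients enrolled

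*Combined protocol and SAP*

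**What the plan says.** Section 6 (Number of Subjects) starts from about 267 consented subjects "to achieve a final sample size of approximately 120 subjects", using 30% for screen failure after consent, 15% for attrition during treatment and 10% for loss to follow-up. The chain is printed as "267 less 30% consented screen fails = 187; 187 less 15% attrition = 147; 147 less 10% loss to follow-up = 120", and the last figure is described as "total participants completing all measures". Table 1 schedules those measures to week 24.

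The Power Analysis paragraph in Section 10 begins: "We propose to enroll 120 patients (60 per group) and considered power to detect a clinically meaningful difference in primary outcome at 6 months". It then claims 80% power for a standardized effect of 0.54 at two-sided 0.05, allowing 10% loss "at the primary endpoint of 6 weeks post-baseline". For the time-averaged effect it claims 0.49 is detectable, with a within-person correlation of 0.6 and "an overall 20% loss to follow-up by week 24 based on our preliminary data".

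On the order of events, Section 4 says that eligibility "will be confirmed by the Independent Evaluator (IE) at the Baseline assessment following consent", and Section 9 (Randomization Procedures) says: "After determining eligibility, enrolled patients will be randomized to treatment groups using a web-based computer generated randomization scheme".

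**The concern.** Two things do not fit.

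- **Arithmetic.** The second and third steps of the Section 6 chain do not follow from the percentages and bases printed beside them. Each is off by 12 people, which is too much for rounding.
- **Meaning of 120.** Section 6 reaches 120 after all losses. The power section starts from 120 and then deducts losses.

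Screen failures are removed after consent and before randomization, so the 187 in Section 6 appear to be the patients available to randomize. Section 6 does not say so, and nothing in the plan reconciles 187 with 60 per group. At stake are how many Veterans to consent, how many to randomize, and when recruitment is complete.

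**Working it through.** **Inputs.** Section 6: 267 consented; rates 30%, 15%, 10%; printed results 187, 147, 120. Power Analysis: 120 enrolled, 60 per group; effect 0.54; two-sided 0.05; 80% power; 10% loss at week 6; 20% loss by week 24; correlation 0.6. Normal approximation unless stated, with 1.960 + 0.842 = 2.8016.

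**1. The chain on its named bases**

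| Step | Calculation | Result | Printed |
|---|---|---|---|
| Screen failure | 267 × 0.70 | 186.9 | 187 |
| Attrition | 187 × 0.85 | 159.0 | 147 |
| Loss to follow-up | 147 × 0.90 | 132.3 | 120 |

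In sequence from the start: 267 × 0.70 × 0.85 × 0.90 = 143.0.

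**2. What does reproduce the print**

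Take all three rates as shares of 267: 267 × 0.70 = 186.9, 267 × 0.55 = 146.9 and 267 × 0.45 = 120.2. In reverse, 120/0.45 = 266.7. Taking 15% and 10% as shares of 187 gives 159 and 140, which does not match. Working back from 120 in sequence gives 120/(0.85 × 0.90 × 0.70) = 224.1, which does not match either.

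The printed figures imply these losses:

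- 187 to 147: 1 − 147/187 = 21.4%
- 147 to 120: 1 − 120/147 = 18.4%
- 187 to 120: 1 − 120/187 = 35.8%

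Section 6's own 15% and 10% in sequence give 1 − 0.85 × 0.90 = 23.5%.

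**3. Which 120 the power section uses**

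Week 6: 2.8016 × √(2/n). Time-averaged over three follow-ups: 2.8016 × √(2/n) × √((1 + 2 × 0.6)/3).

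| Base | Week 6 detectable effect | Time-averaged detectable effect |
|---|---|---|
| 120 randomized, less 10% (54 per arm) and 20% (48 per arm) | 0.539 | 0.490 |
| 120 completing (60 per arm) | 0.51 | 0.44 |
| 187 randomized, less 10% and 20% | 0.43 | 0.39 |
| Printed | 0.54 | 0.49 |

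Only the first row matches, so the power section's 120 are patients allocated, before losses.

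**4. Week 6 power at 0.54 after 10% loss**

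| Randomized | Per arm analysed | Normal | t-test |
|---|---|---|---|
| 120 | 54 | 80.1% | 79.4% |
| 150 | 67.5 | 88.0% | 87.6% |
| 157 | 70.65 | 89.4% | 89.0% |
| 187 | 84.15 | 93.9% | 93.6% |

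**5. Numbers that would be consistent (rounded up)**

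- 120 randomized: 120/0.70 = 171.4, so 172 consented; 120 × 0.90 = 108 at week 6; 120 × 0.80 = 96 at week 24.
- 120 completers, 20% loss by week 24: 120/0.80 = 150 randomized; 150/0.70 = 214.3, so 215 consented.
- 120 completers, Section 6's rates in sequence: 120/(0.85 × 0.90) = 156.9, so 157 randomized; 157/0.70 = 224.3, so 225 consented.

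**The case against.** The strongest reply is that nothing inferential is damaged. Even the corrected chain leaves 143 completers, more than the 108 the power section needs at week 6, and no endpoint or effect size changes. That is right about power. It does not settle which of two very different numbers of patients the trial is to randomize.

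A second reply is that 36% and 20% measure partly different things. Section 6 counts treatment drop-out as well as loss to follow-up, while the power section counts only loss to follow-up, and the plan intends to keep assessing patients who stop treatment. The distinction is real and belongs in the fix. The comparison still stands, because Section 6's 120 are those with complete measures: the printed fall from 187 to 120 is a loss of measurement, and so is the power section's 20%. If patients who stop treatment are still assessed, subtracting them on the way to complete measures needs its own justification.

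Third, the power section says enrolled, not randomized, and Section 9 admits a patient to the intent-to-treat analysis only after a first session is attended. Sixty per group with losses deducted afterwards can hardly mean anything but patients allocated. The first-session condition adds a step for which neither section gives a rate. The 187 remains an inference.

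Finally, the remission example (69% against 42%) does not identify the base: it needs 52 per arm without a continuity correction and 60 with one. The match at 0.54 and 0.49 does not depend on it.

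**Conclusion.** The concern holds. Two of the three printed steps are wrong on the bases they name (147 should be 159; 120 should be 132), and the full chain ends at about 143. The alternative reading, with every rate a share of 267, is not what the text says.

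The number to randomize is 120 by the power section and about 187 by Section 6, a difference of 67, or 56% of 120. The 187 rests on reading consented screen failures as removed before randomization, which Sections 4 and 9 support. The week 6 figures assume no loss between randomization and the first session beyond the stated 10%.

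This must be corrected because the trial relies on its sample size to know when recruitment is complete, and as written that statement is both wrong and contradictory. It does not indicate an underpowered primary comparison.

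**What to change.** Correct the Section 6 chain, and give the consented, randomized and analysed numbers once, in the same words in Section 6 and the Power Analysis paragraph. Attach a base and a time point to each loss rate. Say whether the 15% treatment attrition means missing assessments or only stopping treatment, and whether any loss is expected before the first session. The sponsor should choose one of these:

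- **Power section governs:** about 172 consented, 120 randomized, 108 analysed at week 6 and 96 at week 24.
- **120 completers at week 24 is the target:** about 150 randomized and 215 consented with the power section's 20% loss, or about 157 and 225 with Section 6's 15% and 10% in sequence.
- **All rates are shares of 267 consented:** say so, justify the 36% loss among the 187, and recompute the power section on that base.

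In the same paragraph, change the reference to 6 months to the 6-week primary endpoint that its next sentence and the analysis plan already use.

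The cost is text only. The first option adds no patients to the power section's 120; the second adds 30 or 37 randomized; the third implies about 67 more.

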7. SETTING

Charleston VA Medical Center and surrounding CBOCs.

8. RECRUITMENT METHODS

Research staff will display flyers and posters at the PC clinic and other high-traffic areas. PC providers will be informed of the study and how to refer Veterans to the PCMH provider for treatment of PTSD in the PC setting. The study PCMH provider will be available to referrals from the PC providers as per the standard PCMH procedures. Flyers will direct interested people to contact research staff for information or to inquire about the study with their PCP. Veterans who see flyers for this study and express an interest in being screened and treated for PTSD in PC will be directed to see the study PCMH provider at one of their scheduled walk-in clinics. Provider guidelines for conducting the initial screening of referred patients and discussion of treatment options including study participation is included in the PE-PC Provider manual under heading "Contact 0." In addition, Veterans are routinely screened for PTSD symptoms by their PC provider as per VHA requirements. Individuals who screen positive will be asked if they are interested in participating in research. If so, study staff will screen for PTSD symptoms and significant impairment in function from these symptoms, as well as a desire for treatment to address these symptoms. Potential participants will then meet with a member of the research team and have the study explained to them in a safe and private location with the opportunity to ask any questions. Research staff and the on-site PI will also deliver periodic briefings to PC providers to encourage assessment of PTSD symptoms and increase referrals to PCMH. Research staff and investigators will seek opportunities to brief larger groups such as health fairs, staff meetings, etc.

Minority and Female Recruitment. Inclusion of minorities in PTSD research with Veterans is recognized as being of critical importance. Based on our previous and ongoing RHJ VAMC studies, we estimate that approximately 40% of the sample will be African Americans; 8-10% Hispanic, and 4-6% Asian American; 10% are expected to be women.

